### **1.3.2. Known potential benefits**

This study enrolls metastatic or recurrent patients who have failed standard therapy. Its benefit for patients who participate in this study remains unclear. However, based on prior study of ramucirumab in gastric cancer patients who have failed first-line chemotherapy, ramucirumab monotherapy improves overall survival up to two months[13]. When ramucirumab was tested at different doses in metastatic patients with different cancer types, 60% had stable disease with median duration of 12.7 months[10, 14]. Stable disease  $\geq 4$  months occurred in 20% of patients without warning toxicities. Based on similar mode of action, we expect the activity of HLX06 likely to be similar to that of ramucirumab.

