### 7.3. Follow-up period

After completion of the Treatment period, the patients will have 6 monthly follow-up visits. All patients should complete Follow-up Visit 1 ( $28 \pm 3$  days after the last dose of IP).

The procedures for the follow-up visits are as follows:

1. Physical examination
2. Vital signs
3. ECOG performance status
4. AE assessment
5. 12-lead ECG
6. CBC with differentials and D-dimer
7. Coagulation profile: PT, INR, aPTT
8. Blood chemistry profile: fasting glucose, BUN, creatinine, alkaline phosphatase, ALT, AST, total bilirubin, total protein, albumin, globulin, sodium, potassium, chloride, calcium, magnesium, phosphorus, uric acid, lactate dehydrogenase, IgG and IgM.
9. Thyroid function tests: TSH, T3 and free T4.
10. Urinalysis.
11. Urine pregnancy test for female patients with child-bearing potential
12. Concomitant medications
13. Tumor assessment: if the prior imaging studies are done more than 8 weeks ago)
14. Pharmacokinetic and pharmacodynamic studies.

If the patient refuses or is unable to attend the follow-up visit 1, the reason(s) should be noted in the patient's source documentation.

---

 Every 8 weeks.

 A positive urine pregnancy test needs to be verified by a serum beta-HCG test. Postmenopausal women must be amenorrheic for at least 12 months in order not to be considered of child-bearing potential.

 Only for follow-up visit 1.

Completion of subsequent follow-up visits (Follow-up Visits 2 and beyond) will depend on the status of the patients at the end of treatment. Except for patients who discontinue due to worsening PD, all patients will be followed from the last dose of IP for approximately 6 months until relapse, initiation of a new therapy or the toxicities stabilized or  $\leq$  grade 1. The evaluations performed during the Follow-up Visits will be recorded on the CRF.

Whether or not each patient completes the study drug treatment through the first cycle will be documented on the CRF, including how many doses in Cycle 1 were received. Patients will be considered to have completed Cycle 1 treatment if they completed 4 infusions of IP in Cycle 1 and completed all evaluations at the end of Cycle 1.

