### **8.3. Efficacy evaluation**

The efficacy parameters are the disease control rate (number of patients with CR/PR/SD divided by the total number of patients treated), and objective response rate (ORR) (number of patients with confirmed responses of CR or PR, divided by the total number of treated patients with measurable disease at baseline). Tumor response status will be assessed using RECIST 1

The response to treatment will be assessed in the following schedule:

1. For the first 24 weeks, treatment evaluation is conducted every 8 weeks (regardless of treatment delay).
2. After 24 weeks, treatment evaluation is conducted every 12 weeks

Tumor specific antigen levels (i.e. CEA, CA125, CA19-9, AFP, PSA for prostate cancer) are not used to confirm response, but they will be measured to provide ancillary support for disease response when appropriate in some tumor types.

Efficacy evaluation should use the same modalities. Repeat bone scan for metastatic bone disease is indicated based on clinical judgement by the Investigator.

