#### **Response Confirmation**

To be assigned a status of CR or PR, changes in tumor measurements must be confirmed by consecutive repeat assessments that should be performed no less than 28 days after the criteria for response are first met.

Overall time point responses for all possible combinations of responses in target and non-target lesions with or without the appearance of new lesion.

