**Table 7. Definition of lesions and imaging modality and their requirement**

Definitions	Description
Measurable lesions	Target lesions that can be measured accurately in at least one dimension (longest diameter to be recorded) as $\geq 20$ mm with conventional techniques, or as $\geq 10$ mm with spiral (helical) computed tomography (CT) scan or two (2) times the reconstruction interval (RI) when using spiral (helical) or multidetector CT, but not less than 10 mm.
Non-measurable lesions	Non-target lesions not classified as measurable lesions (longest diameter $<20$ mm with conventional techniques or $<10$ mm with spiral CT scan) and truly non-measurable lesions. These include bone lesions on BS, effusions, and leptomeningeal disease. Any measurable lesions that were not classified as target lesions will be classified as non-target lesions.
Target lesions	
All measurable lesions up to a maximum of 5 lesions and 2 lesions per organ, representative of all involved organs, are to be identified as target lesions and recorded and measured. Target lesions are to be selected on the basis of their size (those with the longest diameter) and their suitability for accurate repeated measurements (either by imaging techniques or clinically).
 
All lesions other than target lesions (or sites of disease) are to be identified as nontarget lesions and are to be recorded. Measurements of these lesions are not required, but the presence or absence of each is to be noted.

Definitions	Description
	
Longest diameter for target lesions - The sum of the longest diameter for all target lesions (SLD).
 
Complete response - Disappearance of all target lesions.
 
Partial response: At least a 30% decrease in the sum of the longest diameter of target lesions, taking as reference the Screening sum longest diameter.
 
Stable disease: Neither sufficient shrinkage to qualify for partial response nor sufficient increase to qualify for progressive disease.
 
Progressive disease: At least a 20% increase in the sum of the longest diameters of target lesions (with addition of diameters of any newly emergent measurable lesions), taking as reference the smallest sum of the longest diameters (nadir) recorded since screening.
 
UE/ND/NA

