Non-target lesions	
All lesions other than target lesions (or sites of disease) are to be identified as nontarget lesions and are to be recorded. Measurements of these lesions are not required, but the presence or absence of each is to be noted.
 
Complete response: Disappearance of all non-target lesions.
 
Incomplete response/stable disease: Persistence of one or more non-target lesion(s).
 
Progressive disease: Unequivocal progression of a non-target lesion or appearance of 1 or more new lesions.

Definitions	Description
	UE/ND/NA
Best overall response	The best overall response is the confirmed overall response. To be assigned a best overall response of partial response or complete response, change in tumor measurements must be confirmed by repeat assessment no less than 4 weeks after the criteria for response of CR or PR are first met.
Methods of measurements	The same imaging modality, method of assessment, and technique must be used throughout the study to characterize each identified and reported lesion.  All measurements are to be made with a ruler or calipers; measurements are to be recorded in metric notation.
Clinical examination	Clinically detected lesions are only to be considered measurable when they are superficial (e.g., skin nodules and palpable lymph nodes). For skin lesions, documentation by color photography—including a ruler to estimate the size of the lesion—is recommended.
Chest X-ray	Lesions on the chest X-ray are to be acceptable as measurable lesions when they are clearly defined and surrounded by aerated lung. Chest X ray is to be performed in full inspiration in the poster-anterior projection. The film to tube distance is to remain constant between examinations. If patients with advanced disease are not well enough to fulfill these criteria, such situations are to be reported together with the measurements. Lesions bordering the thoracic wall, and lesions bordering or

Definitions	Description
	involving the mediastinum, are not suitable for measurements by chest x-ray.

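### Stable disease has no minimum duration, so the disease control rate can count patients scanned soon after one or two infusions, and one week-8 scan cannot be told apart from slow natural growth

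*Combined protocol and SAP*

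**What the plan says.** Table 7 (section 15.4) defines SD for target lesions as "Neither sufficient shrinkage to qualify for partial response nor sufficient increase to qualify for progressive disease". Its upper limit is the progression threshold, "At least a 20% increase in the sum of the longest diameters of target lesions", measured from the nadir.

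Confirmation is tied to response only. The Response Confirmation text reads "To be assigned a status of CR or PR, changes in tumor measurements must be confirmed by consecutive repeat assessments", and the best-overall-response row of Table 7 reads "To be assigned a best overall response of partial response or complete response, change in tumor measurements must be confirmed by repeat assessment". Neither names SD.

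Section 8.3 defines "disease control rate (number of patients with CR/PR/SD divided by the total number of patients treated". Section 11.3.4 uses the same numerator over treated patients with measurable disease. Neither sets a minimum duration for SD. Under section 11.2.4, a single on-treatment tumor evaluation satisfies the post-baseline condition for being response-evaluable.

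Scans are scheduled every 8 weeks for the first 24 weeks, regardless of treatment delay (8.3). Section 7.1 accepts routine-care baseline imaging up to 42 days before the first infusion. All patients should attend Follow-up Visit 1, 28 ± 3 days after the last dose. Its procedures in section 7.3 include "Tumor assessment: if the prior imaging studies are done more than 8 weeks ago". The section 14 schedule marks CT/MRI in the follow-up column without that condition. The study is not randomized (4.4).

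**The concern.** A patient enters with 0% change, which already meets the definition of SD, and leaves that state only by shrinking or growing enough on a scan. With no minimum time, DCR depends partly on when the scan was taken and how fast the tumor would have grown anyway.

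Two problems follow. First, a patient with one or two infusions can enter the numerator on a scan taken about four weeks after the last dose, which says little about the drug. Second, even an on-schedule SD at week 8 rests on one scan in a study with no comparator, so it cannot separate drug effect from slow growth. DCR is a listed secondary endpoint, and readers may take it as an activity signal.

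**Working it through.** The plan states no target or threshold for DCR, so there is no figure of its own to reproduce. The checks are date arithmetic and a growth calculation.

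**1. Timing of Follow-up Visit 1.** Infusions are 7 days apart and the visit is 28 ± 3 days after the last one.
- Stop after one infusion: 0 + 28 ± 3 = 25 to 31 days after first infusion.
- Stop after two infusions: 7 + 28 ± 3 = 32 to 38 days.

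Under 7.3 the scan also needs prior imaging more than 56 days old. At the nominal visit day, the baseline must be more than 56 − 28 = 28 days before first infusion (one infusion) or more than 56 − 35 = 21 days (two infusions). Both fit inside the 42-day window. Under section 14 as written, no such condition applies.

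**2. Growth that still reads as SD.** Assume exponential growth of spherical lesions. A 20% rise in diameter is 1.2³ = 1.728 times the volume, or log₂ 1.728 = 0.789 doublings. With no drug effect, a lesion stays below +20% over t days if its volume doubling time exceeds t/0.789:
- 56 days (day-0 baseline to week 8): 56/0.789 = 71 days
- 98 days (day −42 baseline to week 8): 98/0.789 = 124 days
- 112 days (day-0 baseline to week 16): 112/0.789 = 142 days

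**3. Share of untreated patients who would read as SD.** The documents give no growth rates, so this step is assumption throughout: lognormal doubling times with median m of 50, 75 or 100 days and log-SD 0.8, 5% error on each follow-up measurement, no new lesions, no dropout.

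| Scan pattern | m = 50 | m = 75 | m = 100 |
|---|---|---|---|
| One scan at week 8, day-0 baseline (56 days) | 33% | 51% | 64% |
| One scan at week 8, day −42 baseline (98 days) | 13% | 26% | 39% |
| SD at weeks 8 and 16, day-0 baseline | 10% | 21% | 32% |

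A closed form without measurement error checks the table: P(SD) = Φ(ln(m/T)/0.8), where T is the threshold from step 2. For m = 75 and T = 71, ln(75/71)/0.8 = 0.07, giving 53%. For T = 142, ln(75/142)/0.8 = −0.80, giving 21%.

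In a study of the maximum 30 patients, the first row is about 10, 15 or 19 patients with SD and no drug effect (30 × 0.33, 0.51, 0.64). The third row is about 3, 6 or 10.

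**The case against.** **Follow-up scans may not be meant to count.** Follow-up is a separate period, section 11.2.4 speaks of an on-treatment evaluation, and deteriorating patients without objective progression get their own label under Table 6. This stands in part: the text leaves the question open. But both DCR definitions use treated patients rather than the response-evaluable set, no sentence excludes the follow-up scan, and the place of symptomatic deterioration in DCR is not stated.

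**Best overall response is described as the confirmed response.** That sentence in Table 7 could be stretched to cover SD, but the next one limits confirmation to partial and complete response.

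**On-schedule patients already have a week-8 floor.** True. The 25-to-38-day case arises only after early stopping.

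**Durability is covered elsewhere.** Section 11.3.4 plans Kaplan-Meier PFS, listings and waterfall plots, and makes ORR the primary efficacy parameter. These help a careful reader, but they do not change what DCR counts.

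**Stronger readings a reader might infer:**
- *That the early follow-up scan is an easier growth test.* Under 7.3 it is not. With a day −42 baseline and the nominal visit day, the interval is 42 + 28 = 70 or 42 + 35 = 77 days, and the same model gives SD of 24/41/54% or 20/37/50%, below the fresh-baseline week-8 figures. The defect on that route is minimal drug exposure. A growth interval of only four to five weeks arises only under section 14's unconditioned entry.
- *That section 1.3.2 shows the inflation directly*, through "60% had stable disease with median duration of 12.7 months" against SD of at least 4 "months occurred in 20% of patients without warning toxicities". If these shared one population, half of the 60%, about 30% of patients, would have had SD of 12.7 months or more, which is incompatible with only 20% reaching 4 months. The pair cannot serve as a benchmark.

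**Conclusion.** The point holds as a defect of definition. SD has no minimum time, and DCR counts all of it. DCR can therefore include patients with one or two infusions, and a single week-8 SD in this single-arm study can reflect slow natural growth. Requiring SD at week 16 as well cuts the no-effect rate from 33/51/64% to 10/21/32% under the assumed growth model with a day-0 baseline. Older baselines lower the week-8 rate, to as little as 13/26/39%.

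The timing and the text comparison rest on the documents alone. The doubling-time thresholds rest on exponential, spherical growth, and the percentages on an assumed growth distribution. A reader might go further and say that DCR is mostly a measure of natural growth. The documents give no growth data, so that is not shown.

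DCR is secondary and descriptive, with no decision rule. The MTD and the safety conclusions do not depend on it. This is a cheap improvement.

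**What to change.** In 8.3, 11.3.4 and Table 7:

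1. Count SD toward best overall response and DCR only if documented at the scheduled week-8 scan or later, at least 7 weeks (49 days) after first infusion. The 25-to-38-day follow-up scans then no longer qualify.
2. Class patients whose only scan is an earlier one without progression as not evaluable, and keep them in the denominator as not controlled.
3. Report alongside it disease control at 16 weeks: no progression at the week-8 and week-16 scans.
4. Reconcile the follow-up imaging condition in 7.3 with the unconditioned entry in section 14.

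Item 1 changes the result only for early stoppers. Item 3 is what addresses slow natural growth, and it reduces the problem without removing it, as the 10/21/32% shows.

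The cost is wording only, since the scans are already scheduled. The downside is a lower reported DCR. The rule should be set before response data are reviewed, because the choice changes the rate.

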#### **7.2.5. Discontinuation of patients from treatment**

Each patient has the right to withdraw from the study any time. Patients MUST discontinue Investigational Product (and non-investigational product at the discretion of the Investigator) for any of the following reasons:

- Withdrawal of informed consent (patient's decision to withdraw for any reason)
- Any clinical adverse event (AE), laboratory abnormality or inter-current illness, which, in the opinion of the investigator, indicates that continued participation in the study is not in the best interest of the patient.
- Pregnancy or beginning breastfeeding
- Termination of the study by the Sponsor
- Loss of ability to freely provide consent through imprisonment or involuntarily incarceration for treatment of either a psychiatric or physical (e.g., infectious disease) illness
- Poor compliance with protocol.
- Discretion of the investigator.
- Disease progression or clinical deterioration that no further benefit from treatment is likely (clinical deterioration should be guided by clinical observation described in Section 6.2 and Investigator's judgment).
- Dosing delays longer than 28 days

All patients who discontinue should comply with protocol specified follow-up procedures as outlined in Section 7.2.5 . The only exception to this requirement is when a patient withdraws consent for all study procedures or loses the ability to consent freely (i.e., is imprisoned or involuntarily incarcerated for the treatment of either a psychiatric or physical illness).

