#### **11.3.4. Efficacy**

The primary efficacy parameter is the objective response rate: (ORR, number of subjects with confirmed responses of CR or PR), divided by the total number of treated subjects with measurable disease at baseline). Tumor response status will be defined according to RECIST 1.1 (Appendix 15.4). To perform an evaluation of anti-tumor activity, BOR outcomes, ORR, and disease control rate (DCR: number of patients with CR, PR, or SD divided by the total number of treated patients with measurable disease at baseline) will be tabulated by overall frequency distribution. Median time to response and duration of response will be summarized for those subjects with confirmed responses, using Kaplan-Meier methods; PFS will be similarly summarized. Listings of individual tumor measurements, tumor burden and % changes in tumor burden will be provided. Changes in tumor burden will be presented graphically for each disease type, e.g. by waterfall or other plots.

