#### **Method**

CT scans (or MRI) will be performed to evaluate tumor response. All measurements should be taken and recorded in metric notation (mm) using a ruler or calipers.

CT and MRI are the best currently available and reproducible methods to measure target lesions and qualitatively assess non-target lesions selected for response assessment. Conventional CT (non-spiral or non-helical) and conventional MRI (MRI performed without fast scanning techniques) should produce images contiguously reconstructed at 10 mm or less. Spiral (helical or multidetector) CT should produce images contiguously reconstructed between 5 and 8 mm.

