#### **Documentation of Target and Non-Target Lesions**

All measurable or target lesions, up to a maximum of 5 lesions per organ and 10 lesions total, representative of all sites of disease, will be identified and measured at baseline and followed as target lesions throughout the study. Target lesions should be selected on the basis of their size (longest diameter) and suitability for accurate reproducibility and measurement on follow-up imaging. The SLD for all target lesions will be calculated and reported as the baseline SLD. The baseline SLD will be used as a reference by which to characterize the objective tumor response at each subsequent tumor assessment timepoint. The smallest sum of the longest diameters recorded since baseline will be used as reference when evaluating for progression. All other lesions (or sites of disease) should be identified as non-target lesions and should be recorded at baseline.

Measurement of these lesions is not required, but the presence, absence, or worsening of each should be documented throughout follow-up.

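### Appendix 15.4 scores progression on a 20% rise over the nadir sum with no minimum absolute growth, so at low tumour burden a change of about 2 mm can count as progression

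*Combined protocol and SAP*

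**What the plan says.** Section 11.3.4 makes the appendix the working definition: "Tumor response status will be defined according to RECIST 1.1 (Appendix 15.4".

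In Appendix 15.4, Table 7 gives this threshold for progression of target lesions: "At least a 20% increase in the sum of the longest diameters of target lesions". The comparison is with the nadir, and the appendix text on target and non-target lesions names the same reference: "The smallest sum of the longest diameters recorded since baseline will be used as reference when evaluating for progression". A parenthesis in the Table 7 definition also brings new lesions into the sum: "with addition of diameters of any newly emergent measurable lesions". Neither place, nor any other part of the documents, attaches a minimum increase in millimetres. CR and PR need a repeat assessment at least 28 days later; no such step is written for progression.

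A measurable lesion is at least 20 mm by conventional techniques, or at least 10 mm by spiral CT, "or two (2) times the reconstruction interval (RI) when using spiral (helical) or multidetector CT, but not less than 10 mm". The CT/MRI row of Table 7 allows a 10 mm lesion only at 5 mm reconstruction, and takes the longest diameter in the axial plane.

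The appendix disagrees with itself in two places:

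- **Spiral CT.** The Method text says "Spiral (helical or multidetector) CT should produce images contiguously reconstructed between 5 and 8 mm"; Table 7 says 5 mm.
- **Target lesions.** The text allows 5 per organ and 10 in total; Table 7 allows 2 per organ and 5 in total.

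Treatment runs until progression (Sections 3.1 and 3.3). Section 7.2.5 lists as a reason for mandatory discontinuation: "Disease progression or clinical deterioration that no further benefit from treatment is likely".

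**The concern.** A purely relative threshold shrinks with the tumour. When the sum of diameters is small, 20% of it is only a few millimetres, and ordinary reading variation may reach that without any growth. Using the nadir as reference adds to this: one low reading becomes the yardstick for every later scan. With no confirmation step, a single high reading settles the call.

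At stake are the summaries that depend on the date or fact of progression: PFS and duration of response (Section 11.3.4), disease control where the call comes at the first scan, and time on treatment. With at most 30 patients, a few false calls would move these summaries.

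The phrase that adds new-lesion diameters to the sum is a separate flaw. Table 6 makes any new lesion progression, and the non-target row of Table 7 repeats this. The phrase therefore cannot change the overall call, and it blurs what the sum contains.

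**Working it through.** **Inputs from the documents.** Threshold 20% of the nadir sum (Table 7). Smallest spiral-CT target lesion: the larger of 10 mm and twice the reconstruction interval (Table 7). Scans every 8 weeks for 24 weeks (Section 8.3), so three scans at weeks 8, 16 and 24.

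**Assumptions, not in the documents.** True size constant; independent normal measurement errors with SD 1.0-1.5 mm per lesion; SD 0.5 mm as a sensitivity value.

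**Step 1: the appendix's own size limits.** 2 × 5 = 10 mm and 2 × 10 = 20 mm, both as stated. At an 8 mm interval the smallest lesion is 2 × 8 = 16 mm.

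**Step 2: growth needed for progression = 0.20 × nadir sum.**

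- One 10 mm lesion: 0.20 × 10 = 2 mm.
- The same lesion after shrinking to 7 mm: 1.4 mm; to 5 mm: 1.0 mm.
- One 16 mm lesion: 3.2 mm.
- Two, three or five 10 mm lesions: 4, 6 or 10 mm. A 2 mm change in just one of them is 2/20 = 10%, 2/30 = 6.7% or 2/50 = 4%, which is not progression.

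**Step 3: first scan, one stable lesion of size L.** Progression is called if the new reading is at least 1.2 times the baseline reading. The variance of (new − 1.2 × baseline) is SD² × (1 + 1.44) = 2.44 SD², so P = P(Z > 0.2L / (1.562 SD)). For L = 10 mm:

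- SD 1.0: P(Z > 1.280) = 10.0%
- SD 1.5: P(Z > 0.854) = 19.7%

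Holding the threshold at exactly 2 mm instead gives P(Z > 2 / (1.414 SD)) = 7.9% and 17.3%.

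**Step 4: three scans against the running nadir** (400,000 simulated patients per setting). Entries are the percentage falsely called progressive by week 24.

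| Stable target lesions | No minimum, SD 1.0 | No minimum, SD 1.5 | 5 mm minimum, SD 1.0 | 5 mm minimum, SD 1.5 |
|---|---|---|---|---|
| one, 10 mm | 37 | 61 | 0.1 | 4.7 |
| one, 15 mm | 13 | 37 | 0.1 | 4.7 |
| one, 20 mm | 3 | 19 | 0.1 | 4.6 |
| two, 10 mm | 16 | 41 | 3 | 20 |
| three, 10 mm | 6.5 | 28 | unchanged | unchanged |
| two, 20 mm | 0.1 | 4.0 | unchanged | unchanged |
| one, 30 mm | 0.04 | 2.7 | unchanged | unchanged |

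At SD 0.5 mm, one 10 mm lesion gives 2.7% with no minimum.

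**Step 5: where a minimum of m mm matters.** It changes the call only if 0.20 × nadir sum < m, that is, below m/0.20. For m = 3 this is 15 mm; for m = 5 it is 25 mm. The 5 mm value is illustrative only.

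**The case against.** The strongest reply is that this is a corner case resting on an assumed error. The rule applies to the sum, all measurable lesions up to the cap are followed, and the largest are chosen. Two 20 mm lesions or one 30 mm lesion give at most about 4%. The measurement SD is not in the documents, and at 0.5 mm even the single 10 mm lesion gives only 2.7%. All of this stands and limits the point to low tumour burden. A minimum is also only a partial remedy: three 10 mm lesions give 6.5-28% with or without a 5 mm floor.

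Some stronger readings are tempting but not supported:

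- **That the appendix demonstrably drops a minimum which RECIST 1.1 requires.** The documents cite the guideline (reference 25) but do not reproduce its progression rule. Whether it sets a minimum, and at what value, has to be checked there.
- **That 2 mm is noise because it is below the 5-8 mm CT interval.** A 10 mm lesion is allowed only at 5 mm, and the interval is slice spacing, whereas diameters are axial. It is not a measurement error.
- **That disease control falls by the week-24 rates.** The rate counts CR, PR or SD, with no minimum duration of SD stated. A false call at week 16 or 24 after SD at week 8 does not lower it; only the first-scan rate can.
- **That the new-lesion phrase distorts the waterfall plots.** The sum is defined separately over target lesions. The phrase is redundant and ambiguous, but no distortion is shown.

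**Conclusion.** The point holds for patients with a small nadir sum. As written, Table 7 scores any 20% rise over the nadir as progression, and 2 mm is enough when a single 10 mm lesion is the whole sum. For one truly stable lesion of 10-20 mm, false progression by week 24 ranges from about 3% to 61% over SD 1.0-1.5 mm, and is far lower at SD 0.5 mm. These figures depend on the assumed SD, independent errors and three scans; the absence of a minimum depends on none of them.

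The reach is limited. PFS is descriptive and not a listed endpoint; duration of response and disease control rate are secondary. The primary endpoints (adverse events and MTD) and the maximum of 30 patients do not use this definition. For hepatocellular carcinoma a footnote in the synopsis names mRECIST instead. This merits correction before efficacy is assessed, but does not threaten the dose-finding result.

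**What to change.** 1. Reconcile the progression definition in Table 7 with the RECIST 1.1 guideline the plan cites (reference 25), by adding to the 20% rule the absolute minimum increase that guideline specifies. Take the value from the guideline; the 5 mm used above only illustrates size. If a purely relative rule is intended, say so and give the reason.
2. Delete the phrase adding newly emergent lesion diameters to the sum. Tables 6 and 7 already make any new lesion progression.
3. In the same pass, settle the two internal conflicts: target lesions at 5 per organ and 10 in total versus 2 per organ and 5 in total, and spiral CT at 5-8 mm versus 5 mm.
4. Because progression also governs discontinuation (Section 7.2.5), the sponsor's clinical team should confirm that the reconciled definition is the one meant there. No stopping rule is proposed here.

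The cost is a few sentences in an appendix, with no change to sample size or visits. The downside is that a few true small progressions would be called one scan later.
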